7.1.2 Clinical Procedures/Assessments

7.1.2.1 Physical Examination

A full physical examination will be performed at screening and at the end-of trial or discontinuation visit. Focused physical examinations will be performed during the trial, as specified in the Trial Flow Chart (Section 6.0). Focused physical examination will involve an examination for abnormalities of the heart/lungs, abdomen, extremities, and genitourinary exam. Only abnormal findings should be recorded on eCRFs, either as medical history (present at the screening visit) or as an adverse event (new findings during the trial). Refer to Section 7.2 for instructions on adverse event reporting.

These exams should be conducted by a licensed clinician (i.e., physician, physician's assistant, or nurse practitioner).

7.1.2.2 Vital Signs, Height, and Weight

Vital signs (including HR and BP), body weight and height will be obtained at screening and at subsequent visits specified in the Trial Flow Chart (Section 6.0).

BP and *HR* will be measured (to be performed in duplicate) using an electronic blood pressure monitor.

Body weight will be measured (to be performed in duplicate) using a calibrated digital scale.

Height will be measured (to be performed in triplicate) using a wall-mounted calibrated stadiometer. The Sponsor will calculate growth velocity of height based on these measurements.

For details on measuring techniques, refer to Section 12.7.

7.1.2.3 Testicular Ultrasound

A testicular ultrasound scan (USS) should be performed at protocol specified visits (see Section 6.0, Trial Flow Chart) to assess the testicular volume and testicular sonographic pattern. To avoid variability, the site should designate a single staff member who is trained in the technique of testicular ultrasound to perform the exam whenever possible. The same ultrasound equipment should be used throughout the trial.

At Visit 1/Screening, testicular ultrasound images will be read locally by the investigator (if qualified) or a local radiologist with appropriate training and expertise in reading testicular ultrasound. This local reader will calculate testicular volume to evaluate Inclusion Criterion #5, and evaluate the ultrasound for any presence of local pathology that would exclude the subject from participating (see Section 5.1.3 Subject Exclusion Criteria). Testicular volume is calculated using the formula for prolate ellipsoid, i.e., $[\pi/6] \times (\text{longitudinal}) \times (\text{antero-posterior}) \times (\text{transverse})$ diameters. The screening ultrasound assessment made by the site should be recorded on the source document. Additionally, the testicular ultrasound of each testis will be evaluated by the investigator or a local radiologist with appropriate training and expertise in reading testicular ultrasound for any pathological findings throughout the trial. These findings will be recorded on the source document, and reported in the eCRF as a pre-existing condition in the medical history (if noted at screening), or as an adverse event (if new findings during the trial). Refer to Section 7.2 for instructions on adverse event reporting.

All testicular ultrasound images will be sent to a Sponsor-validated central imaging vendor to be read in a masked manner after the subject completes participation in the study to assess study endpoints (i.e., testicular volume and sonographic pattern). The central imaging vendor will assess adequacy of all submitted ultrasound scans; if a scan is deemed inadequate, the site will be contacted and a repeat scan requested. The ultrasound images will be read by the central imaging vendor according to the description in the Independent Review Charter for imaging to calculate the total testicular volume (i.e., the sum of left and right testes). The process for image collection and transmission to the central imaging vendor can be found in the Site Imaging Manual. The evaluation of the echogenicity will also be made by the vendor according to criteria described in the Independent Review Charter for imaging.

7.1.2.4 Tanner Staging of Pubertal Development

At protocol specified visits (see Section 6.0, Trial Flow Chart), Tanner Staging will be assessed by genital development and pubic hair distribution as noted in Section 12.6. The investigator will use clinical assessment to assign the Tanner Stage for pubic hair and Tanner Stage for genital growth (e.g., penile length and scrotum development) separately. The investigator will perform testicular ultrasound to measure testicular parameters as according to the procedures outlined in Site Imaging Manual provided to the investigator site. However, the Tanner Stage for testicular volume will not be assessed clinically by the investigator and will be completed by the central imaging vendor according to the method described in the Independent Review Charter for imaging. Each score will be considered independently and there will not be a composite score.

7.1.2.5 Adverse Events Monitoring

Adverse events will be monitored throughout the trial. Refer to Section 7.2 for details.

7.1.3 Laboratory Procedures/Assessments

Details regarding specific laboratory procedures/assessments to be performed in this trial are provided below. The total amount of blood to be drawn over the course of the trial (from pre-trial to post-trial visits), including approximate blood volumes drawn by visit and by sample type per subject can be found in Section 12.4.

7.1.3.1 Laboratory Safety Evaluations (Hematology and Chemistry)

Laboratory tests for hematology and chemistry to be performed by a central laboratory are specified in [Table 4](#). Blood samples for safety laboratory tests should be taken pre-dose, i.e., prior to administration of MK-8962 or hCG on the day of the visit, whenever possible.

See the Trial Flow Chart (Section 6.0) for the sampling times. For handling, storage and shipment of these samples please refer to the Central Laboratory Manual.

Table 4 Laboratory Tests

Hematology	Chemistry	Other
Hematocrit	Albumin	Free T4
Hemoglobin	Alkaline phosphatase	
Platelet count	Alanine aminotransferase (ALT)	
WBC (total and differential)	Aspartate aminotransferase (AST)	
	Bicarbonate	
	Calcium	
	Chloride	
	Creatinine (for determination of eGFR)	
	Glucose (non-fasting)	
	Phosphorus	
	Potassium	
	Sodium	
	Total Bilirubin	
	Direct Bilirubin, if total bilirubin is elevated above the upper limit of normal	
	Total protein	
	Blood Urea Nitrogen	

eGFR: estimated glomerular filtration rate

7.1.3.2 Panel of Endocrine Parameters

The following hormones will be assessed by the Sponsor designated central laboratory: FSH, LH, hCG, inhibin-B, AMH, Total T, calculated free T, E2 and SHBG. All blood sample collection for endocrine parameters should be performed prior to injection(s) of MK-8962 or hCG on the day of visit, if there is any injection(s) scheduled for that day.

See the Trial Flow Chart (Section 6.0) for the sampling times. For handling, storage and shipment of these samples please refer to the Central Laboratory Manual.

Note: The LH and FSH assays that are part of the optional GnRHa stimulation test or GnRH IV infusion test as described in Inclusion Criterion 8 (Section 5.1.2) should be performed by the local laboratory; refer to local laboratory instructions as appropriate.

7.1.3.3 Pharmacokinetic Evaluations

A total of 13 serum samples for assessment of MK-8962 concentration will be collected at specified time points indicated in Section 7.1.3.3.1, Flow Chart of Pharmacokinetic Assessments. For handling, storage and shipment of these samples please refer to the Central Laboratory Manual. Concentrations of MK-8962 in serum will be determined using a validated assay.

7.1.3.3.1 Flow Chart of Blood Sample Collection for Pharmacokinetic Assessments of MK-8962^a

Scheduled Week	Scheduled Study Day	Visit Number	Time [range]	Sample Number
0	1	V2	15 minutes prior to first MK-8962 injection	01
0	1	V2	6-24 h after first dose ^b	02
1	3	V3	32-52 h after first dose and -at least 12 hours after sample 02^b	03
1	5	V4	+96 ±24 [72-120] h after first dose ^b	04
1	8	V5	+168 ±24 [144-192] h after first dose ^b	05
2	11	V6	+240 ±24 [216-264] h after first dose ^b	06
4	29	V8	Predose to 3 rd MK-8962 injection ^c	07
12	85	V9	Predose to 7 th MK-8962 injection and prior to 1 st hCG injection ^c	08
24	169	V11	Predose to 13 th MK-8962 injection and prior to hCG injection ^c	09
36	253	V12	Predose to 19 th MK-8962 injection and prior to hCG injection ^c	10
48	337	V13	Predose to 25 th MK-8962 injection and prior to hCG injection ^c	11
64	449	V15	--	12
--	--	Discontinuation (if Subject did not complete V15)	--	12
Post 7 days	--	Follow-up	--	13

^a Blood serum samples for MK-8962 will be processed according to the central laboratory procedures outlined in their manual for handling biological samples. The timing of each sampling is to be recorded on the eCRF.
^b Samples 02 through 06 may be obtained at any time-point within the specified time frame. The timing of each sampling is to be recorded on the eCRF.
^c A visit window of ±3 days is allowed.

7.1.3.4 Anti-MK-8962 Antibodies

Serum samples will be collected for the assessment of anti-MK-8962 antibodies. Baseline samples MUST be taken prior to the first dose of MK-8962. See the Trial Flow Chart (**Section 6.0**) for the sampling times. All blood sampling for antibodies should be performed prior to injection(s) of MK-8962 or hCG on the day of visit, if there is any injection(s) scheduled for that day.

For handling, storage and shipment of these samples please refer to the Central Laboratory Manual.

7.1.3.5 Future Biomedical Research Sample Collection

The following specimens are to be obtained as part of Future Biomedical Research:

- Leftover main study serum from endocrine parameters, anti-MK-8962 antibodies, and PK for MK-8962 concentration stored for future research

7.1.4 Other Procedures

7.1.4.1 Withdrawal/Discontinuation

Subjects who discontinue/withdraw from treatment prior to completion of the treatment regimen should be encouraged to continue to be followed for all remaining study visits.

When a subject discontinues/withdraws from participation in the trial, all applicable activities scheduled for the Discontinuation Visit should be performed at the time of discontinuation. Any adverse events which are present at the time of discontinuation/withdrawal should be followed in accordance with the safety requirements outlined in Section 7.2 - Assessing and Recording Adverse Events. Refer to Section 7.1.5.3 on how to manage patients who discontinue study medication but who do not withdraw consent.

7.1.4.1.1 Withdrawal From Future Biomedical Research

A Subject's consent for Future Biomedical Research may be withdrawn by the subject or the subject's legally acceptable representative (as appropriate). Subjects may withdraw their consent for Future Biomedical Research and have their specimens and all derivatives destroyed. A subject's consent may be withdrawn. Subjects may withdraw consent at any time by contacting the principal investigator for the main trial. If medical records for the main trial are still available, the investigator will contact the Sponsor using the designated mailbox ([contact]), and a form will be provided by the Sponsor to obtain appropriate information to complete specimen withdrawal. Subsequently, the subject's specimens will be removed from the biorepository and be destroyed. A letter will be sent from the Sponsor to the investigator confirming the destruction. It is the responsibility of the investigator to inform the subject of completion of destruction. Any analyses in progress at the time of request for destruction or already performed prior to the request being received by the Sponsor will continue to be used as part of the overall research trial data and results. No new analyses would be generated after the request is received.

In the event that the medical records for the main trial are no longer available (e.g., if the investigator is no longer required by regulatory authorities to retain the main trial records) or the specimens have been completely anonymized, there will no longer be a link between the subject's personal information and their specimens. In this situation, the request for specimen destruction cannot be processed.

7.1.4.2 Blinding/Unblinding

This is an open label trial; there is no blinding for this trial.

7.1.4.3 Domiciling

No domiciling is required. At Visit 2/Day 1, the first and second PK serum samples will be collected at two time points: one at about 15 minutes before the first dose of MK-8962, another at 6-24 hours after the first dose of MK-8962. Subjects will report to the site in the morning for the pre-dose blood sample collection. Subject is not required to remain at the site to wait for the collection of the second PK sample, as long as he returns within the window of 6-24 hours after first MK-8962 injection to have the second PK sample collected.

7.1.4.4 Calibration of Equipment

The investigator or qualified designee has the responsibility to ensure that any device or instrument used for a clinical evaluation/test during a clinical trial that provides information about inclusion/exclusion criteria and/or safety or efficacy parameters shall be suitably calibrated and/or maintained to ensure that the data obtained is reliable and/or reproducible. Documentation of equipment calibration must be retained as source documentation at the trial site.

7.1.5 Visit Requirements

Visit requirements are outlined in Section 6.0 - Trial Flow Chart. Specific procedure-related details are provided above in Section 7.1 - Trial Procedures.

7.1.5.1 Screening

At V1 (approximately 7 days prior to treatment allocation), potential subjects will be evaluated to determine that they fulfill the entry requirements as set forth in Section 5.1. Screening safety labs may be repeated once per protocol if results are inconsistent with the subject's clinical status or any other recent laboratory evaluations. The period between V1 and treatment allocation (V2) is up to 6 weeks. This time limit may be increased under special circumstances after the site obtains the agreement from the Sponsor.

Subjects may only be rescreened once.

7.1.5.2 Treatment Period

The Study Days when the visits should be scheduled are prespecified in Section 6.0 (Trial Flow Chart). Subjects should adhere to the visit schedule described in the Flow Chart as much as possible.

The allowed windows for the sampling time of each of the 13 PK samples are designated in Section 7.1.3.3 (Flow Chart of Pharmacokinetic Assessment). The first PK sample should be collected approximately 15 minutes before the first witnessed dose of MK-8962, and samples #02 to #06 are to be collected within the window after first MK-8962 dose, as specified in the PK Flow Chart. For subsequent PK assessment visits V8 to V13 (corresponding to the collection of PK samples #07 to #11, respectively), a scheduling window of up to 3 days is allowed.

For V8 (corresponding to the collection of PK sample #07), if a subject is to adjust the visit by up to 3 days (e.g., returns to the clinic 3 days earlier or 3 days later than the prespecified Scheduled Study Day in the Trial Flow Chart), the site should ensure that blood samples

(including PK samples) are collected prior to the witnessed injection of MK-8962 at that visit.

For PK assessment visits V9 through V13, if the subject returns to the clinic up to 3 days earlier or up to 3 days later than the prespecified Scheduled Study Day in the Trial Flow Chart, he should keep his regularly scheduled injection of MK-8962 and not change it to correspond to the PK visit. For example, if the subject is to delay V9 (prespecified for Day 85 in the Trial Flow Chart) by three days to Day 88, the site should remind the subject to administer the home-injection of his 7th MK-8962 dose as originally scheduled (i.e., on Day 85 according to the Trial Flow Chart), and return to the clinic on Day 88 for collection of PK sample #08. The actual timing of each injection and each PK sample collection should be accurately documented, whether or not any variation to the protocol-specified schedule occurs.

Subjects should adhere to their hCG injection schedules independent of the visit deviations or altered MK-8962 dosing schedules discussed above. PK sample #12 is to be collected at study completion (V15) or discontinuation (D/C), and the last PK sample (#13) is to be collected at the post-treatment follow-up visit.

For visits where no PK samples are collected (V7, V10, and V14), a 7-day visit adjustment window is allowed. If a non-PK visit is adjusted to a non-prespecified Study Day, the subject should not change his regular injection schedules of MK-8962. When an adjustment in the schedule is required for a specific visit, this should not impact subsequent visits and the schedule for subsequent Study Days should remain as specified in the Trial Flow Chart. This is to ensure adherence to the 64 week treatment period for this study.

There may be cases where visits need to be scheduled outside the allowed visit window. These should be rare incidences. In these cases, the subjects should be scheduled as soon as possible to the required time point, taking into consideration a subject's supply of the trial medication.

Phone visits are required visits and should be conducted within the protocol-specified time frame (see Section 6.0).

Any visits scheduled outside the specified visit window for that particular visit is not considered a major protocol deviation and the Sponsor does not need to be contacted for approval.

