It is anticipated, based on matured kidney elimination and metabolic drug clearance systems, that PK data of adolescent males aged 14 years or older will be similar to PK data of adult males. To further support the expectation that PK data will be similar, PK sampling will be performed in the current study in adolescent males to confirm predicted exposure levels.

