5.2.2 Timing of Dose Administration

MK-8962

Throughout the 64-week treatment period, a single dose of MK-8962 100 μ g (body weight \leq 60 kg) or 150 μ g (body weight $>$ 60 kg) is to be administered subcutaneously in the abdominal wall once every two weeks in the morning on the same day of the week throughout the trial. The fixed day of the week is chosen by the subject depending on individual preference. For the convenience of visit scheduling, a weekday injection is preferred, as most protocol-specified site visits fall on the same day of a scheduled MK-8962 administration. The time and dose of MK-8962 administration should be recorded in a paper diary.

Note: The subject should adhere to the same MK-8962 injection schedule (e.g., on every other Monday, etc.) throughout the trial, whenever possible. In the event that the subject misses a dose on a scheduled dosing day (e.g., a holiday, etc.), the make-up dose should be administered as soon as possible, and can only be administered within one week immediately following the missed dose. Otherwise, the missed dose should be skipped and the subject should continue on with the next regularly scheduled injection.

hCG

Starting from the last day of Week 12 (Day 85), hCG is to be injected twice a week in the morning, on fixed days of the week throughout the trial. The scheduling of hCG injection should be coordinated with the MK-8962 injection, as illustrated in [Table 3](#) below. After addition of the solvent to the freeze-dried substance, the reconstituted hCG solution should be administered by subcutaneous injection. The time and dose of hCG administration should be recorded in a paper diary. Note that [Table 3](#) is meant for illustration only, and the subject, in consultation with the investigator, may utilize any schedule that meets dosing interval requirements for hCG and MK-8962.

Note: The subject should adhere to the same twice-weekly injection schedule throughout the trial. In the event that the subject misses a scheduled hCG dose, the make-up dose should be administered as soon as possible, up to the day before the next scheduled injection day. This instruction for the handling of a missing hCG dose should be followed whether or not the subject also misses the MK-8962 dose at the same time.

Table 3 MK-8962 and hCG Dosing Schedule

Examples of Dosing Schedule Scenario	MK-8962 100 µg or 150 µg	hCG ^a
A	Every other Monday	Every Monday and Thursday
B	Every other Tuesday	Every Tuesday and Friday

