8.5.2 Safety Analysis Populations

The All-Subjects-as-Treated (ASaT) population consists of all randomized subjects who received at least one dose of MK-8962 and will be used for the analysis of safety data in this study.

At least one laboratory or vital sign measurement obtained subsequent to at least one dose of study treatment is required for inclusion in the analysis of each specific parameter. To assess change from baseline, a baseline measurement is also required.

All-Subjects-Pharmacokinetically-Evaluable (ASPE) population: Consists of all subjects from the ASaT group, for whom at least one PK parameter can be calculated according to the protocol and who did not have any protocol violation interfering with PK. Subjects included in the ASaT group, but excluded from the ASPE group will be listed including the reason(s) for exclusion.

The final determination on major protocol deviations interfering with PK, and thereby the composition of the ASPE population, will be made prior to the finalization of the database and will be documented in a separate memo.

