8.6.3.3 Pharmacokinetic Analysis

The PK analysis will be conducted in the ASPE group.

For characterization of MK-8962 PK in adolescents, serum samples will be collected at specific time points throughout the study (see flowchart in Section 6.0).

Serum MK-8962 concentrations will be obtained using a solid phase enzyme-immunoassay specific for MK-8962. Descriptive statistics for the serum concentrations by time-point will be calculated and will comprise number of observations (n), number of missing or substituted observations, arithmetic mean together with standard deviation and coefficient of variation, geometric mean together with coefficient of variation, minimum, median and maximum.

The existing PopPK model in HH men will be updated using the serum MK-8962 concentration data obtained in the current study. A covariate analysis will be performed to identify important relationships between PK parameters (ka MK-8962, CL MK-8962, V MK-8962, f MK-8962, and FSH baseline) and patient characteristics (i.e., gender, body weight, height, BMI, age). The updated model will be used to derive estimates for at least the following PK parameters in adolescent males: AUC_{ss}, C_{max_ss}, C_{min_ss}, Cl and V. Descriptive statistics for the PK parameters will be calculated and will comprise number of observations (n), arithmetic mean, standard deviation and arithmetic coefficient of variation, geometric mean and geometric coefficient of variation, minimum, median and maximum.

In addition, through the PopPK approach, analysis will be performed using the serum MK-8962 concentration data obtained in this study relative to prior studies in adult HH men and in women to identify possible differences in MK-8962 PK between females, HH men and adolescent males. It was identified based on the HH adult men PopPK analysis that MK-8962 clearance was 30% lower in male subjects as compared to female subjects. The updated PopPK model in adolescent males will be used to validate the assumptions also apply to adolescent males. This analysis will be reported separately.

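### Late visits at Weeks 12, 24, 36 and 48 yield post-dose MK-8962 samples under a predose label, and Section 8.6.3.3 has no rule to separate them

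*Combined protocol and SAP*

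**What the plan says.** - **Dosing.** Section 5.2.2 gives MK-8962 "once every two weeks in the morning on the same day of the week throughout the trial".
- **Sample labels.** In Section 7.1.3.3.1, sample #08 (V9) is predose to the 7th injection. Samples #09, #10 and #11 (V11, V12, V13) are predose to the 13th, 19th and 25th "MK-8962 injection and prior to hCG injection". A footnote to these samples and to #07 states: "A visit window of ±3 days is allowed".
- **Moved visits, V9 to V13.** Section 7.1.5.2 tells the subject to leave the injection on its scheduled day. In the example of a V9 delayed by three days, he gives himself the "7th MK-8962 dose as originally scheduled (i.e., on Day 85 according to the Trial Flow Chart), and return to the clinic on Day 88" for sample #08.
- **Moved visit, V8.** The same section has the site make sure that the blood samples, "including PK samples) are collected prior to the witnessed injection of MK-8962 at that visit".
- **Analysis.** Section 8.6.3.3: "Descriptive statistics for the serum concentrations by time-point will be calculated". The list includes arithmetic and geometric means, SD, CV, median and range. It also updates the population PK model and derives steady-state exposure parameters from it.
- **PK population.** Section 8.5.2 limits the ASPE set to subjects with at least one calculable PK parameter and "who did not have any protocol violation interfering with PK".
- **Purpose.** Section 4.2.3.3: "PK sampling will be performed in the current study in adolescent males to confirm predicted exposure levels". PK is secondary objective 6 in Section 3.2.

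**The concern.** The label and the late-visit instruction cannot both hold. If the visit is late and the injection is not, the blood is drawn after the injection, yet predose is the only time-point description the sample has. A summary by time-point would then mix values from the end of one dosing interval with values from shortly after the next injection.

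The output at stake is the descriptive MK-8962 concentration table at Weeks 12, 24, 36 and 48, mainly the means, SD, CV and maximum. Readers will take the predose rows as observed troughs, and a trough level (of FSH immunoreactivity) was the main dose-selection criterion in Section 4.2.2. Comparison over time suffers too. A late V8 lengthens the time since dose, while a late V9, V11, V12 or V13 cuts it to a few days. The concern does not extend to hCG timing, antibody, endocrine or FSH data.

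**Working it through.** **1. Reproduce the schedule.** Dose k falls on Day 1 + 14(k − 1).

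- k = 7: 1 + 14 × 6 = 85
- k = 13: 1 + 14 × 12 = 169
- k = 19: 1 + 14 × 18 = 253
- k = 25: 1 + 14 × 24 = 337

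These are the flow chart's days for V9, V11, V12 and V13. V10 has no PK sample.

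**2. Time since the last dose at V9, with dose 6 on Day 71 and dose 7 held on Day 85.**

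| Day of visit | 82 | 83 | 84 | 85 | 86 | 87 | 88 |
|---|---|---|---|---|---|---|---|
| Days since last dose | 11 | 12 | 13 | 14 | 1 | 2 | 3 |

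Day 85 is taken as drawn before the injection. The same pattern holds at Days 169, 253 and 337. At V8 the injection moves with the visit, so a draw on Day 32 is 32 − 15 = 17 days after dose 2 and is still predose.

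**3. Look for a rule that would catch this.** Section 8.6.3.3 has none based on time since dose. ASPE works on whole subjects with violations, and a visit inside the window is not a violation. Section 7.1.5.2 adds that even a visit outside its window is not a major deviation.

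**4. Size, as an illustration.** Section 4.2.2 supplies the structure: one compartment, first-order absorption. Section 4.1.1 gives half-life and time to peak only relative to recFSH, so the values are assumed: half-life 2 to 5 days, tmax 1 to 3 days, absorption faster than elimination, full 3-day delay. At steady state with τ = 14 days,

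C(t) ∝ exp(−ke·t)/(1 − exp(−ke·τ)) − exp(−ka·t)/(1 − exp(−ka·τ)),

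where ke = ln 2 / half-life and ka solves tmax = ln(ka/ke)/(ka − ke).

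Worked case: half-life 3 days and tmax 3 days give ka = 2ke.

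- C(3) ∝ 0.5/0.9606 − 0.25/0.9984 = 0.270
- C(14) ∝ 0.0394/0.9606 − 0.00155/0.9984 = 0.0394
- Ratio = 6.8

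| Half-life (days) | tmax (days) | C(3 d)/C(14 d) |
|---|---|---|
| 2 | 1 to 2 | 45 to 30 |
| 3 | 1 to 3 | 12.7 to 6.8 |
| 4 | 1 to 3 | 6.7 to 4.9 |
| 5 | 1 to 3 | 4.6 to 3.8 |

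A tmax of 3 days cannot occur with a 2-day half-life under these assumptions.

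**5. Effect of one late sample on a visit's summary.** If the other values sit at the 14-day level, the geometric mean is multiplied by ratio^(1/n).

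| Ratio | n = 10 (planned completers) | n = 15 (planned enrolment) |
|---|---|---|
| 3.8 | 1.14 | 1.09 |
| 12.7 | 1.29 | 1.18 |
| 45 | 1.46 | 1.29 |

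The arithmetic mean is multiplied by 1 + (ratio − 1)/n. For n = 10 that is 1 + 2.8/10 = 1.28 up to 1 + 44/10 = 5.4.

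**6. Comparators.** A visit 3 days early is a true predose draw with C(11 d)/C(14 d) = 1.5 to 2.8. One in 10 multiplies the geometric mean by 1.04 to 1.11. A V8 held 3 days late gives C(17 d)/C(14 d) ≈ 2^(−3/half-life), that is 0.35 to 0.66.

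**The case against.** The strongest reply is that the analysis serving the stated purpose is protected. Adolescent exposure parameters, including Cmin_ss, come from the population PK model. The protocol requires actual injection and sampling times to be recorded, so the model can place a late sample correctly. What remains is a descriptive table for a secondary objective in a trial that tests no hypothesis. This stands and limits the point to that table.

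Second, Section 8.6.3.3 says only that summaries are by time-point. It does not say that late draws will be averaged with predose ones, it foresees a count of missing or substituted values, and a supplemental SAP may add detail. Pooling is indeed a reading of the text. It is the natural one, because predose is the only description these samples have and no rule for handling late ones is given.

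Third, the contrast with V8 has a reason: that dose is witnessed on site, whereas later doses may be given at home on a fixed schedule. That explains the instruction but leaves the label wrong.

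Fourth, the multiples rest on assumed PK values and every ratio above 12.7 comes from half-lives under 3 days. The median would move little with a single late sample. Both are correct.

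Fifth, removing post-dose samples does not make the rest uniform. Two visits 3 days early among 10 would raise the geometric mean by about 9 to 23% (1.51^(2/10) to 2.83^(2/10)), which overlaps the effect of one late visit. This is why time since dose should be shown for every listed value.

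**Conclusion.** The point holds. That a late visit gives a post-dose sample under a predose label follows from the schedule and from the protocol's own Day 85 and Day 88 example. It needs no PK assumption, only that the subject injects on the scheduled day as told.

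The size is conditional. Under the assumed half-life of 2 to 5 days and tmax of 1 to 3 days, one sample drawn 3 days late raises a visit's geometric mean by 14 to 46% with 10 subjects and by 9 to 29% with 15. For half-lives of 3 to 5 days the ranges are 14 to 29% and 9 to 18%. Late-visit frequency is unknown, so the effect on the final table cannot be predicted. Early and late visits both raise the Week 12 to 48 values, so they do not cancel.

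The primary endpoint is untouched, and so are the population PK estimates if actual times are used. This should be corrected before the PK data are summarised.

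**What to change.** In Section 8.6.3.3:

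- Classify samples #08 to #11 by recorded time since the last MK-8962 injection.
- Admit only true pre-injection samples within the window to the predose summaries.
- List post-dose samples separately and use them, with actual times, in the population PK model.
- Print the time since last dose beside every listed concentration, including #07, so that early draws and late V8 draws are visible.

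Then reconcile the predose labels in Section 7.1.3.3.1 with the late-visit instruction in Section 7.1.5.2.

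The cost is a few lines of SAP text and one derived variable from times already collected. The predose tables may lose a few values.
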